1. INTRODUCTION

1.1 Background

Physical inactivity is a major global driver of non-communicable disease and all-cause mortality.¹ It is associated with increased frailty,² dementia risk,³ and reduced physical function,⁴ is a condition of socio-economic inequality, and is more prevalent in older adults.⁵ Moreover, physical activity (PA) and inactivity is related to social relationships: our previous work in the CHARIOT Covid Rapid Response (CCRR) study suggested that older adults who were lonely or who had markers of social isolation reduced their physical activity during the Covid-19 pandemic.^{6,7} In contrast, people in more active social networks and in relationships are more likely to be physically active,⁸ and social support that is specific to physical activity is associated with increased PA levels in older adults.⁹

Physical activity interventions in older adults improve balance, muscle strength and reduce the risk of falling, and can also help older adults perform activities of daily living.^{10–12} Moreover, digital interventions specifically can increase physical activity levels in older adults. A systematic review suggested that such interventions increase moderate to vigorous PA by approximately 35% of recommended amounts. However, it is unclear how long this effect might last.¹³ Generally, studies assessed the impact of an intervention when it ends, and systematic reviews suggest that most non-digital approaches to increase PA, although effective, have an unknown duration of impact beyond one year.¹⁴

One concept that might bridge the gap between intervention and longer-term impact is that of physical literacy. This encapsulates the competence and confidence with physical skills, motivation towards physical activities, and the value a person attributes to physical movement.¹⁵ It is still not understood how physical literacy in older adults translates into increased and sustained physical activity.¹⁶ This pilot and feasibility study of a digital rehabilitation tool, that follows rehabilitation principles using the principles of key movement domains, aims to assess the impact on physical activity levels, markers of physical literacy, the physical and mental health, wellbeing and function over a 6-month period, with the aim to extend to longer time-periods as resources and capacity allow. This aligns with the Medical

Research Council (MRC) guidance for the development and evaluation of complex interventions, with feasibility testing an integral and important component.¹⁷

1.2 Study Rationale

Aims:

- This project aims to pilot, and assess the feasibility of, a randomised controlled trial using a digital rehabilitation tool to enhance physical activity and literacy in older adults

Research questions:

- What are the impacts and effect sizes of the intervention on the proposed primary outcome (self-reported physical activity levels (MET minutes/week) at 3 and 6 months) and secondary outcomes (mood/physical literacy scores/frailty/quality of life)?
- What is the acceptability of the digital tool for participants?
- For how long do people use the tool, and how frequently (adherence)?
- What is the recruitment rate?
- What is the attrition rate to follow-up?
- What issues are encountered when cleaning and analysing data?
- What are outcomes at longer time intervals (1-2 years)?
- What is the safety profile of the tool for participants?
- What are the perceptions of participants on the usability and acceptability of the digital tool?

Hypothesis:

- Use of the digital tool will be safe and feasible for participants, with impacts on their physical activity and physical literacy at 3 and 6 months

2. STUDY OBJECTIVES

The primary study objective is to pilot a randomised controlled trial of a digital rehabilitation tool and to assess the feasibility for a larger randomised controlled trial. Objectives will cover:

- (i) Impact on effect sizes (pilot RCT): for both the proposed primary outcome on self-reported physical activity (MET/minutes per week) and secondary outcomes of physical literacy and mood
- (ii) Safety: self-reported safety profile
- (iii) Feasibility: recruitment rate, attrition rate, follow-up rate for questionnaires; adherence and usage of the digital tool
- (iv) Usability: perceptions of usability and impact; perceived barriers to inclusion

3. STUDY DESIGN

The study design is a pilot and feasibility randomised controlled trial for the impact of a digital tool for physical activity in older adults on their physical activity and physical literacy versus simple educational resources alone. Participants will be recruited from the Cognitive Health in Ageing Register for Investigational and Observational Trials (CHARIOT) register: a cohort of over 40,000 cognitively healthy (without a known diagnosis of dementia) adult volunteers aged over 50 years, recruited from 172 GP surgeries across West and North London as part of a collaboration between regional GP practices and the School of Public Health, at Imperial College London.

Upon expression of interest and informed consent, participants will be:

1. Asked to complete questions using the qualtrics platform on: financial status, social connections, physical activity levels, illnesses and alcohol and smoking habits and perceptions of physical activity (physical 'literacy') (all described in more detail below). Postcode will be asked to understand socioeconomic background of those participating.

2. Randomised to either the intervention or control group.

3. Receive either a link to a digital physical activity intervention that is web-based (the intervention), or an information sheet linking to advice and guidance on physical activity (the

control group). They will be asked to follow the guidance in these tools only for as long as they feel comfortable doing so.

4. Asked to repeat the online questionnaires at 3 and 6 months, and to consent to longer-term follow-up.

Further details on the specific aspects are described below.

3.1 Intervention and control

3.1.1 Movement Foundations digital rehabilitation tool

Participants in the intervention group will receive links to access a digital rehabilitation tool as a web-based app. The Movement Foundations digital tool was initially designed and created between in 2021 by an Imperial College London team supported by Imperial Health Charity Innovate funding (grant reference number II2021_7), and updated in 2022 to focus on older adults, supported by Imperial College London and National Institute of Health Research (NIHR) Biomedical Research Centre (BRC) funding (reference 5899469). The web-based rehabilitation platform Rehab Guru was commissioned to develop the platform for the digital rehabilitation tool in both instances.

The digital tool consists of low-impact and intensity exercises based on functional movement patterns, a graduated progression in terms of volume (number of sessions per week and number of repetitions of exercises) and intensity/load (difficulty of exercise) (Figure 1). Users will be entered onto a starting level based on an algorithm adjusted for the number of sit to stand (STS) repetitions over 1 minute, and the perceived degree of effort this exercise requires (Borg CR10 scale). Levels of exercise are phased: each phase lasts one to two weeks and contains a variable number of sessions. For each phase, users are able to choose exercises ranging in difficulty and across functional movement pattern domains. When users log individual exercise sessions, they are asked to rate their perceived effort, and their subjective assessment of adherence to the exercises (how much were they able to do of what they intended).

Users are asked to complete daily questionnaires on: fatigue, sleep, muscle soreness and emotional stress, based on Hooper and Mckinnon scoring criteria.¹⁸ An additional domain of recovery has also been added. At the end of each phase, scores from the daily questionnaires, the level of effort and degree of subjective and objective adherence to the sessions are combined by an algorithm developed by the study team to generate options to the user. These include: progressing to the next phase; consolidating the previous phase; regressing a phase; and signposting for medical advice. In addition, a resource hub provides participants with information on deconditioning, planning sessions, rest and recovery, fatigue, sleep and muscle soreness. Users will be encouraged and guided to set goals for physical activity development. Users have the option of sharing goals on a public noticeboard (without identifiable information), and providing encouragement to other users using a thumbs-up symbol. The combination of information, social, review and reward, action planning and instruction align with items from the CALO-RE taxonomy for behaviour change for physical activity interventions,¹⁹ and the Capability, Opportunity, Motivation-Behaviour (COM-B) model for behaviour change (Figure 2).²⁰

[figure not shown]

Figure 1: The digital tool supports the user with exercises across movement domains, daily feedback on user responses, goal setting, and visual feedback on progress

[figure not shown]

Figure 2: Alignment with the Capability, Opportunity, Motivation-Behaviour (COM-B) model

Those in the control arm will receive an online-accessible and downloadable document with educational resources, including the UK Chief Medical Officer guidance for physical activity in older adults, and links to NHS guidance for physical activity.

Follow-up will be at 3-months initially, but we will ask participants to consent to subsequent follow-up at 6-months, and again at 1-year and 2-years as funding and research capacity allow.

4. PARTICIPANT RECRUITMENT

4.1 Pre-recruitment evaluations

4.1.1 Study population, recruitment strategies and baseline pre-screening

Figure 3 depicts the flow of recruitment, screening and baseline assessment procedures. Participants will be recruited from the Cognitive Health in Ageing Register for Investigational and Observational Trials (CHARIOT) register. The CHARIOT Register (n ≈ 40,000) was initiated in 2011 through collaborative efforts between GP practices across West London with the Department of Primary Care and Public Health and the Ageing Epidemiology (AGE)

Research Unit, both within the School of Public Health at Imperial College London. The register is comprised of a cohort of approx. 40,000 cognitively healthy older adults aged 50-85 years who expressed interest in being contacted for participation in studies relating to dementia prevention and healthy ageing. In addition, participants will be recruited through public advertisement including through social media. Participants will be recruited over a period of 1 month from ~~1st March~~ May 2023 and halted at a maximum of 1000 participants across both groups (500 per group).

All participants will be invited to join the study through an email of a flyer on an invitation email distributed through the secure Imperial Qualtrics platform to eligible people on the CHARIOT register. The distribution list will be managed such that automated follow-ups will be sent at 3 and 6 months, provided the participant has not opted out of the study. . If no response is received, an automated follow up email will be sent. A study-specific email address will be provided to potential participants ([contact]) should they wish to ask any further questions, and it will be made clear to participants that they can opt out or withdraw from the study by clicking the dedicated link. The invitation flyer on the email / letter will include a unique link connected to a participants study (CHARIOT) ID number, which will direct them to the Qualtrics Platform, and will also contain an ~~and~~ embedded dedicated study ID also to pseudoanonymise respondents. Distribution will be managed via Qualtrics by the AGE team. On clicking the link/scanning the QR code, participants will receive a welcome message and will be prompted to read the Participant Information Sheet. The welcome message and Participant Information Sheet will outline the pilot's eligibility criteria for participants to do a self-screening assessment and will request participants to only progress onto completing the Informed Consent Form (ICF) if they fulfil all eligibility requirements. Prior to the ICF, participants will be asked to confirm that they meet the eligibility requirements.

4.1.2 Randomisation

Once consent is complete, the participant will be provided with the baseline questionnaire, and then randomised evenly by the Qualtrics platform to either receive ²¹a link to the digital Movement Foundations physical activity tool (intervention arm), or to download the educational resources (control arm).

4.1.3 Blinding

Although it will be difficult to blind informed participants from their allocation to intervention or control, single blinding of analysts will be performed until all data at 3 and 6 months have been cleaned. Therefore, the study IDs allocated to the intervention or control group will be withheld from the study team cleaning and analysing the data, and held only by the data controller at the Ageing Epidemiology Unity (AGE).

4.1.4 Follow-up and study flow

Follow-up questionnaires (the same as baseline questionnaires but without demographic information, and with added components on safety and feasibility) will be sent to each participant at 3 months from completion of the baseline questionnaire, and again at 6 months using the Qualtrics platform Funding will be sought to send further follow-up questionnaires at 1 year and again at 2 years, and these follow-up windows will be included in consent process at the start of the study.

[figure not shown]

Figure 3: Study flow

Participants will be recruited and randomised following informed consent. Randomisation will be to intervention (Movement Foundations digital tool) or control groups (educational resources only) at a 1:1 rate. All participants will receive baseline questionnaires at time=0, mid-point questionnaires at time=3 months, and end-point questionnaires at time=6 months.

4.1.5 Data analysis

The primary outcome is change in self-reported physical activity (MET minutes per week) from baseline to 3 and 6 months. The effects on secondary outcomes including physical literacy, mood, frailty and sleep will also be assessed, as will participant usage of the digital tool, and drop out rates. An intention to treat analysis will be used. Although this study is designed to assess effect sizes for primary and secondary outcomes, using a previous study with of a physical activity intervention with similar outcomes,²² we performed a power calculation for two-sided t-test of means of two samples with alpha error of 5%. Standard deviation of both groups was assumed to be ~550 (*). The 95% confidence interval sizes for the control and test groups are about 43 (48.7 - 5.7) and 27 (136.6 - 109.7), respectively. This translates into group standard deviations of $(43/4) * \sqrt{3000}$ and $(27/4) * \sqrt{3000}$. For conservativeness, we used a higher value of $15 * \sqrt{3000}$ for both groups. The results are shown in Figure 4 and Figure 5. For a mean difference of 150 MET minutes/week between groups, which would be clinically significant, and power of 0.8, approximately 5700 participants between groups would be required.

[figure not shown]

Figure 4: Power vs Mean Difference

Y-axis is the study power between 0 and 1 (100%). The x axis shows the assumed values for the difference of the group means. We tried various combinations of the sample size of each group (assumed to be equal) and effect size.

[figure not shown]

Figure 5: Power vs. sample size

Y-axis is the study power between 0 and 1 (100%). The x axis shows a range of sample sizes between 100 to 1500. We tried various combinations of the sample size of each group (assumed to be equal) and effect sizes.

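### The primary outcome is a change score with no baseline adjustment stated; adjusting for baseline activity would sharpen the effect estimate without new data

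*Protocol*

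**What the plan says.** Protocol section 4.1.5 (Data analysis) defines the outcome: "The primary outcome is change in self-reported physical activity (MET minutes per week) from baseline", taken to 3 and 6 months. For the analysis it gives only the principle: "An intention to treat analysis will be used". It names no model and no covariate.

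The one comparison of arms appears in the power paragraph: "we performed a power calculation for two-sided t-test of means of two samples with alpha error of 5" per cent. That paragraph gives two standard deviations, "Standard deviation of both groups was assumed to be ~550" and "For conservativeness, we used a higher value of $15 * \sqrt{3000}$ for both groups", and a target: "For a mean difference of 150 MET minutes/week between groups, which would be clinically significant, and power of 0.8".

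Section 4.1.2 sets the order of events: "the participant will be provided with the baseline questionnaire, and then randomised evenly by the Qualtrics platform". Section 4.1.4 repeats the same questionnaires at 3 and 6 months, without the demographic items. Section 6.1.1 names the IPAQ short form, a self-report tool, as the activity measure. Section 4.1.1 caps recruitment at 1000 (500 per group).

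**The concern.** Estimating effect sizes is objective (i) in section 2 and the first research question in section 1.2, so the width of the interval around the activity effect matters in this pilot.

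A plain comparison of mean changes subtracts the whole baseline value, which fixes its coefficient at 1. When baseline and follow-up self-reports correlate below 1, that over-corrects. The noise in the baseline measurement enters the estimate, and a chance difference between arms at baseline shifts it. Estimating the coefficient from the data avoids both effects. Baseline is measured before allocation, so it is a legitimate covariate.

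If the outcome definition is carried into the analysis with the only test the protocol names, the interval will be wider than the data require.

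**Working it through.** **Inputs.** From section 4.1.5: difference 150 MET-min/week, two-sided alpha 5%, power 0.8, SD about 550 or 15 × √3000 = 821.6. From section 4.1.1: 500 per arm at most. The correlation r is my assumption, shown as a range.

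**The plan's own figure.** n per arm = 2 × (1.96 + 0.8416)² × (SD/150)² = 15.70 × (SD/150)².
- SD 821.6: 15.70 × 30.0 = 471 per arm, 942 in total.
- SD 550: 15.70 × 13.44 = 211.1, rounded up to 212 per arm, 424 in total.

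Neither gives the roughly 5700 in section 4.1.5. That mismatch is a separate matter. The figures below use the stated inputs, not the 5700.

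**Variance ratio.** Let baseline and follow-up each have variance s² and correlation r.
- Raw change: 2s²(1−r).
- Adjusted for baseline: s²(1−r²).
- Ratio: (1−r²) / [2(1−r)] = (1+r)/2, a reduction of (1−r)/2.

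With unequal SDs, s_x at baseline and s_y at follow-up, the raw change variance exceeds the adjusted one by (s_x − r·s_y)². That is never negative, so apart from one degree of freedom adjustment does not lose precision.

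**Size, reading the stated SD as the SD of change.** The adjusted SD is SD × √((1+r)/2). Example at r = 0.5: 821.6 × √0.75 = 711.5; standard error 711.5 × √(2/500) = 45.0; 150/45.0 − 1.96 = 1.37; power 91.5%.

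| Assumed r | Variance reduction | n per arm for 80% power (SD 821.6) | Power at 500 per arm (SD 821.6) | 95% half-width at 500 per arm (SD 821.6) | Same half-width (SD 550) |
|---|---|---|---|---|---|
| raw change | none | 471 | 82.3% | 101.8 | 68.2 |
| 0.2 | 40% | 283 | 96.1% | 78.9 | 52.8 |
| 0.3 | 35% | 307 | 94.7% | 82.1 | 55.0 |
| 0.5 | 25% | 354 | 91.5% | 88.2 | 59.0 |
| 0.7 | 15% | 401 | 87.9% | 93.9 | 62.9 |
| 0.8 | 10% | 424 | 86.1% | 96.6 | 64.7 |
| 0.9 | 5% | 448 | 84.2% | 99.3 | 66.5 |

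With SD 550, raw-change power at 500 per arm is already 99.1%, so there the gain shows only in the interval width.

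**Other reading of the SD.** The protocol does not say whether its SD describes change or single-occasion values. If 821.6 is a single-occasion SD, then at r = 0.3 the SD of change is 821.6 × √1.4 = 972 and the adjusted SD is 821.6 × √0.91 = 784. Power at 500 per arm is about 68% for raw change and 86% adjusted. The variance ratio is still 0.65.

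**The case against.** The strongest reply is that the protocol does not commit the analysis to a t-test. A reader might infer that it does, but the test appears only as the basis of the power calculation. The analysis itself is described only as intention to treat. That stands.

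A change outcome also does not exclude adjustment. Regressing change on arm and baseline gives the same treatment estimate as regressing the follow-up value on arm and baseline. That stands too. Models and covariates are commonly left to an SAP, which is not shown here and may already specify this, so the absence of a covariate is not in itself an error.

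A reader might infer that the raw comparison is biased or badly exposed to imbalance. Under randomisation it is unbiased. At 500 per arm the standard error of the baseline difference is √(2/500) = 0.063 SD, so chance imbalance will usually be small. Nor does the protocol say that allocation is unstratified: sections 4.1.2 and 4.1.4 give an even 1:1 split and neither describe nor rule out stratification.

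What remains is that the protocol fixes the form of its primary outcome and sizes the trial on an unadjusted comparison, in the section headed as data analysis, without saying how the baseline value will be used.

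**Conclusion.** The point holds as a recommendation on efficiency. It does not show that the plan is invalid. Adjusting for baseline reduces the variance relative to a raw change comparison by (1−r)/2 under equal variances, from 40% at r = 0.2 to 5% at r = 0.9. A single band such as 15–35% is tempting, but it amounts to assuming r between 0.7 and 0.3, and nothing in the protocol supports that range.

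The power gain at 500 per arm (82.3% to 94.7, 91.5 or 87.9% for r = 0.3, 0.5 or 0.7) needs 821.6 to be the SD of change. A reader might conclude that the trial has no power to spare without adjustment. The documents do not support that in general: section 4.1.5 also states about 550, where unadjusted power is about 99%, and the protocol gives no attrition figure.

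**What to change.** Add one sentence to section 4.1.5: the primary estimate is the between-arm difference in MET-min/week at 3 and 6 months, adjusted for baseline MET-min/week. The model can be ANCOVA on the follow-up value, the equivalent regression of change on arm and baseline, or a mixed model for both visits with baseline as covariate and arm-by-time terms. Unadjusted mean change can still be reported descriptively, so the outcome as now defined is kept.

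Use the same adjustment for the continuous secondary scores (HADS, PSQI, SPPLI). FRAIL, which section 6.1.1 groups into robust, pre-frail and frail, needs a model for ordered categories with baseline as covariate.

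The cost is that sentence, a matching line in the SAP if one exists, and the analysis code. No new data are needed. Reporting the observed r would also help to size the larger trial.

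### The stated requirement of about 5700 participants does not follow from the protocol's own inputs, which give 944 in total (SD 822) or 426 (SD 550)

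*Protocol*

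**What the plan says.** Section 4.1.5 (Data analysis) describes the calculation in these terms: "we performed a power calculation for two-sided t-test of means of two samples with alpha error of 5" per cent. The SD appears twice. First: "Standard deviation of both groups was assumed to be ~550". Then, after SDs are derived from the confidence intervals of an earlier physical activity trial: "For conservativeness, we used a higher value of $15 * \sqrt{3000}$ for both groups".

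The target difference is given as "For a mean difference of 150 MET minutes/week between groups, which would be clinically significant", and the conclusion is "and power of 0.8, approximately 5700 participants between groups would be required". The legends of Figures 4 and 5 say the two groups were taken as equal in size, and section 4.1.4 specifies 1:1 randomisation. The Figure 5 legend adds: "The x axis shows a range of sample sizes between 100 to 1500".

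Section 4.1.1 says recruitment will be "halted at a maximum of 1000 participants across both groups (500 per group"). Section 4.1.5 mentions no allowance for dropout or clustering.

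**The concern.** All the inputs to the calculation are in one paragraph, so the result can be checked directly, and 5700 looks far too large. A difference of 150 against an SD of 822 is a standardised effect of about 0.18. Against an SD of 550 it is about 0.27. Effects of that size need hundreds of participants in total, not several thousand.

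This is the protocol's only statement of how many participants are required. Section 2 makes assessing the feasibility of a larger trial part of the primary objective. Taken literally, the sentence says the cap of 1000 supplies 1000/5700 = 17.5% of the required number. A reader would conclude that this study can say almost nothing about a 150-unit difference, and that a definitive trial must be very large. Neither conclusion follows from the protocol's own assumptions.

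**Working it through.** **Inputs (section 4.1.5 unless noted).** Two-sided two-sample t-test; alpha 0.05; power 0.80; difference δ = 150 MET minutes/week; equal groups (also section 4.1.4). SD either 15 × √3000 = 821.6, the value said to be used, or about 550. The SDs derived from the earlier trial are (43/4) × √3000 = 588.8 and (27/4) × √3000 = 369.7. Both are below 821.6.

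**Required size.** By the normal approximation, n per group = 2 × (1.960 + 0.842)² × SD² / δ², where (1.960 + 0.842)² = 7.849.

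- SD 821.6: SD² = 225 × 3000 = 675,000, and 675,000 / 22,500 = 30. So n = 2 × 7.849 × 30 = 470.9, or 471 per group. The exact t-test solution is 471.9, or **472 per group, 944 in total**.
- SD 550: SD² = 302,500, and 302,500 / 22,500 = 13.44. So n = 2 × 7.849 × 13.44 = 211.1, or 212 per group. The exact t-test solution is 212.01, or **213 per group, 426 in total**.

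Ratios to the stated figure: 5700 / 944 = 6.0 and 5700 / 426 = 13.4.

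**Attempts to reproduce 5700.** None of the following came within 3% of it, read as a total or per group:

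| Variation (SD 822 unless noted) | Total |
|---|---|
| Power 0.90 | 1262 |
| Power 0.95 | 1560 |
| Alpha 0.01 | 1402 |
| 944 inflated for an assumed 50% dropout | 1888 |
| Full interval width as the standard error, 43 × √3000 as SD | 7742 |
| Full interval width as the standard error, 27 × √3000 as SD | 3052 |

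**Working backwards from 5700.** SD = δ × √(n/2) / 2.802.

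- As a total (n = 2850): 150 × √1425 / 2.802 ≈ 2021.
- As a per-group number (n = 5700): about 2858.

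The largest SD in the protocol is 822. With 2850 per group, power at 150 exceeds 99.9% for either SD. The difference detectable with 80% power would be 2.802 × SD × √(2/2850), which is 61 for SD 822 and 41 for SD 550.

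**Against Figure 5.** The plotted range ends at 1500. Neither 2850 nor 5700 lies within it; 213 and 472 both do. The curves themselves were not available to check.

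**What the cap gives.** Power is for δ = 150 with SD 822. The 95% CI half-width is 1.96 × 821.6 × √(2/n). The retention values are assumptions.

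| Analysed per group | Retention | Power | Half-width (MET min/week) |
|---|---|---|---|
| 500 | 100% | 82% | 102 |
| 425 | 85% | 76% | 111 |
| 350 | 70% | 67% | 122 |

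With SD 550, power at 500 per group is 99%. With SD 822, 80% power at the cap needs retention of at least 472/500 = 94.4%.

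**The case against.** The best defence is that 5700 is a slip of the keyboard or of editing rather than a failed calculation. The protocol still carries visible struck-out text in section 4.1.1, and two values such as 500 and 700 could have been run together. A figure near 500 per group would sit close to the computed 472, match the cap and fall inside Figure 5. This cannot be excluded, but no struck-out text appears in section 4.1.5, and the sentence refers to participants across both groups. As totals, 500, 570 and 700 give power of only 0.53, 0.59 and 0.67 with SD 822. A slip would need the same correction in any case.

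The 13-fold ratio rests on the SD of about 550, whereas the section says a higher value was actually used. That is fair: the comparison with the stated calculation is the six-fold one. The larger ratio is relevant only because the section also gives 550 as its assumption.

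The study is a pilot, its cap is not derived from 5700, and nothing says 5700 will size the later trial. This stands, and it limits the consequence. That a definitive trial would be mis-sized is a risk, not an established result.

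Finally, no units are given for the earlier trial's intervals, so the SD of 822 holds only if they are in MET minutes per week. This is a reason to confirm the SD, but it does not rescue 5700.

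**Conclusion.** The stated requirement is wrong as written. On the SD the protocol says it used, it is six times too large (5700 against 944). On the other stated SD it is 13.4 times too large (5700 against 426). The conclusion depends only on inputs in section 4.1.5 and on reading the SD as being in the same units as the 150 MET minutes/week difference. It does not depend on the choice between the t-test and the normal approximation, or on a dropout allowance of up to 50%.

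The error does not alter recruitment, randomisation or the planned analysis. It does misstate how the 1000-participant cap relates to the difference of interest: on the conservative SD the cap gives about 82% power with complete follow-up, and less with attrition.

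**What to change.** In section 4.1.5:

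1. State one SD, with its units, after reconciling about 550 with 15 × √3000.
2. Replace the 5700 sentence with the size recomputed from that SD. If 822 is confirmed, suitable text would be: with an SD of 822 and a difference of 150 MET minutes/week, 472 analysed per group (944 in total) give 80% power at two-sided 5% alpha. If 550 is confirmed, the figures are 213 and 426.
3. Add what the cap delivers. With SD 822, 500 analysed per group gives 82% power and a 95% CI half-width of about 102 MET minutes/week; 350 per group, an assumed 70% retention, gives 67% and about 122.
4. Check Figures 4 and 5 against the same inputs and say whether the Figure 5 axis is per group or total.

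The cost is a wording change and, if needed, redrawn figures. No extra participants are required.
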